5.1 Screening

Screening for patients will begin on December 14, 2015 at 9am and end in approximately one year when the appropriate sample size has been reached. All open tibia fractures arriving at the MOI emergency room during the enrollment period will be screened for inclusion in the study. All patients, even those who are excluded, need to have their information recorded on REDCAP.

The orthopedics department has been directed to call the study phone whenever an open tibia patient comes in. The research coordinator is required to keep the study phone close with them at all times.

- If the patient arrives during normal business hours (7am to 5pm), the coordinator will go to the emergency room to assist the patient's physician with screening. The coordinator is also expected to periodically check the emergency room for any new open tibia patients in case the emergency staff fail to contact the study phone.
- The study coordinator on duty will remain at MOI until 9pm and periodically check the emergency room for any new open tibia admissions. If the patient arrives from 9pm to 11pm, the coordinator will screen from home using the study laptop. If the patient meets study inclusion/exclusion criteria, the coordinator will come to the hospital to consent the patient to enroll in the study.

Inclusion Criteria

1. Skeletal maturity
2. AO/OTA 42 open tibia fractures *
3. Wound primarily closeable (no flap or delay in closure due to contamination needed)
4. Palpable pedal pulses (no vascular injury sustained)
5. Presentation within 24 hours from injury **

Exclusion Criteria

1. Current injury is a pathologic fracture
2. Sustained bilateral tibia fracture
3. Sustained comminuted femur fracture
4. Sustained severe Traumatic Brain Injury (GCS<12) ***
5. Sustained severe spinal cord injury (lower extremity paresis/paralysis)
6. Sustained severe burns (>10% total body surface area (TBSA) or >5% TBSA with full thickness or circumferential injury)
7. Prior ipsilateral leg injury requiring surgery
8. Prior or current lower limb deformity or abnormality
9. Unable to complete follow-up visits

* See addendum for OTA42 subclassification schematic

** Patients who present greater than 24 hours after injury and/or have non-primarily closeable wounds but meet all other criteria are eligible for the cohort study (see below)

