*** If at any point prior to the operation, the patients GCS score drops below 12, the patient will be excluded from the study. If the GCS score drops below 12 after the operation, the patient will remain in the study.

Cohort Study

Patients who meet all inclusion/exclusion criteria but present to MOI's emergency room beyond 24 hours after their injury and/or have non-primarily closeable wounds will be consented and included in a separate cohort study. These patients will be treated exactly the same way as an RCT patient with the same data collected except that they will not be randomized. Their primary surgeon will decide which operation is the most appropriate. The same consent form will be used, but the patient will be explained the details of the cohort study rather than the RCT study.

Informed Consent

All patients who remain eligible after clinical screening will be offered enrollment in the study. A written informed consent document will be provided to the patient and reviewed in detail by a trained research coordinator. This document will be provided in English or Swahili depending on the patient's preference. In cases where the participant is unable to provide consent, consent will be obtained from a legally acceptable representative. If the participant is unable to read, verbal consent will be provided in the presence of an impartial witness. The consent document should be signed and dated by the individual providing consent as well as the participant or their legally acceptable representative.

Signed consent forms should be kept in the SIGN Nail Office. A picture of the signature form should be taken and uploaded onto REDCAP.

If there is any concern from either the patient and/or the research coordinator that the patient will be unlikely to complete any follow-up visits (especially the 1 year follow-up visit), that patient will be excluded from the study. If the patient does not provide consent for any other reason besides an inability to complete follow-up clinics, the reason for not providing consent will be recorded.

Baseline Clinical Information

Once a participant has completed informed consent, the research coordinator will obtain baseline clinical information and record the information in REDCAP.

Antibiotics Administration

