5.4 Wound Measurement and Classification

A measurement of the wound is to be done in the operating room. Specifically, it should be taken after the patient receives anesthesia and the temporary splint/bandages have been removed but just before surgical debridement. The wound should be measured using a centimeter ruler (rather than visually approximated) and recorded onto REDCAP.

Only the maximum dimension of the wound (the longest length possible) needs to be recorded. This is irrespective of how the wound is oriented along the limb. The wound length should only include the part of the wound that is open (ignore any superficial abrasions that may be connected to the open part of the wound).

OTA Wound Classification

Classification of the wound is done using the OTA Wound Classification questionnaire (see REDCAP section). Wound classification is to be done after surgical debridement which allows the surgeon to fully assess the wound.

Wound Closure Status Check

After surgical debridement, the surgeon will assess the wound to see if the wound can be primarily closed. If the wound can be primarily closed, the patient will continue with the RCT Study.

If the wound cannot be primarily closed, the patient will be enrolled as a cohort study patient.

If the wound is found to be primarily closeable and came to MOI within 24 hours of injury, the patient will be funneled into the RCT study and randomized

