5.7 Definitive Treatment

Nail: It is up to the surgeon’s discretion as to the appropriate size of the nail. A total of 4 screws will be placed – 2 proximal and 2 distal. These decisions will be recorded on REDCAP during the operation.

Exfix: Two Schanz screws will be placed proximally and two will be placed distally; only a single bar will utilized. The patient will be instructed on proper pin-care procedures at the time of discharge which involves pouring methylated spirit (alcohol) directly onto the pins twice daily until the exfix is removed. The patient will be discharged with bandages covering the wound, but the pin insertion sites will be left open to allow for proper ventilation and pin-care. The patient will be discharged with dressing covering the wound and pin sites. The exfix will remain on for 3 months. At the 3 month follow-up, the decision will be made to (1) remove ex-fix, (2) remove ex-fix and replace with cast, (3) delay exfix removal, or (4) other. Delayed removal or other will be submitted for adjudication review.

Wound Protocol

If the wound is dry at the 2 week wound check, the dressing will be removed. If the wound is still wet at 2 weeks, the dressing will be changed and the patient will be instructed to periodically revisit the hospital to change the dressing until the wound becomes dry.

Weight Bearing Protocol

All patients will be advised to be on toe-touch status for the first 6 weeks. Afterwards, the patient will be instructed to bear weight as permitted by pain.

Summary of Treatment Options

Primarily closeable?	->	No	->	Cohort Study
	->	Yes (Cohort) (+ damage control)	->	Temporary exfix
	->	Yes (Cohort) (no damage control)	->	Definitive operation
	->	Yes (RCT): Nail (+ damage control)	->	Temp exfix (then nail)
	->	Yes (RCT): Exfix (+ damage control)	->	Temp exfix (then exfix)
	->	Yes (RCT): Nail (no damage control)	->	Nail now
	->	Yes (RCT): Exfix (no damage control)	->	Exfix now

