6.2 Intra-operative/Discharge Form

This form applies to both RCT and cohort patients. But for cohort patients, the randomization module will not appear.

1. Wound measurement

- a. A measurement of the wound should be performed after the patient receives pain medication and after all bandages and dressings have been removed. Take the maximum dimension of the portion that is open, ignoring superficial abrasions
- b. The measurement should be done in centimeters using a ruler rather than visually approximated. Be as precise with the measurement as possible

2. Surgical Debridement and Primary Closure status

- a. Whether or not the surgeon believes the wound can be primarily closed is done after surgical debridement. They will clean up the wound, manipulate the fracture, and see if there is enough skin to close the wound.
- b. If the surgeon believes the patient can be primarily closed, the patient passes the last exclusion criteria check and should remain in the study. If it is a cohort patient, it is up to the surgeon which operation the patient receives. If it is an RCT patient, proceed to the randomization module

Has the wound been surgically debrided?		
<small>* must provide value</small>		
 Yes  No		
reset		
Does the surgeon believe this patient is primarily closeable?		
 Yes  No		
This is a key study question		
<small>* must provide value</small>		

- c. If the surgeon believes the wound is not primarily closeable, the patient needs to be excluded from the study. This is considered an "intra-operative exclusion". This is what the warning message looks like:

Subject is **NOT** eligible for the RCT study anymore.

This patient is considered an "intraoperative exclusion". Save the form as "Complete". Do not change any information that has already been collected.

Subject is **NOT** eligible for the cohort study anymore.

This patient is considered an "intraoperative exclusion". Save the form as "Complete". Do not change any information that has already been collected.

3. Randomization (RCT ONLY)

- a. If the patient is a cohort patient, the following reminder message will appear indicating the randomization module is hidden for these patient

Subject is a **PROSPECTIVE COHORT** patient. The randomization module will not appear. Please complete the remaining questions.

The patient has been enrolled in the wrong study.

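### Section 6.2 excludes a patient whose wound proves non-closeable after debridement, while 5.4 and the 5.7 table enrol that patient in the cohort

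*Protocol*

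**What the plan says.** Section 6.2 (Intra-operative/Discharge Form) opens by stating its scope: "This form applies to both RCT and cohort patients". Closeability is judged after surgical debridement (item 2a). If the wound can be closed, item 2b says that "the patient passes the last exclusion criteria check and should remain in the study", and then tells staff what to do next for a cohort patient and for an RCT patient. If it cannot, item 2c says: "If the surgeon believes the wound is not primarily closeable, the patient needs to be excluded from the study". The case is labelled an intra-operative exclusion. Two warning boxes follow. One ends RCT eligibility; the other says the subject is not "eligible for the cohort study anymore". Both tell staff to save the form as complete and to leave the data already collected unchanged.

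Section 5.4 (Wound Closure Status Check) covers the same moment and says: "If the wound cannot be primarily closed, the patient will be enrolled as a cohort study patient". The Summary of Treatment Options in 5.7 reads: "Primarily closeable? -> No -> Cohort Study".

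The general eligibility rules agree with 5.4. The note to the inclusion criteria in 5.1 says: "Patients who present greater than 24 hours after injury and/or have non-primarily closeable wounds but meet all other criteria are eligible for the cohort study". The Cohort Study paragraph in 5.1 says that otherwise eligible patients who present "beyond 24 hours after their injury and/or have non-primarily closeable wounds will be consented and included in a separate cohort study". The automated screening message in 6.1 (item 5) also returns cohort eligibility for a non-closeable wound, with or without late presentation.

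**The concern.** A coordinator in theatre works from the form guide. Followed literally, 6.2 removes from all follow-up a patient whom 5.4 says to enrol. It would also remove someone who entered the cohort precisely because the wound could not be closed. Non-closeable wounds are one of the two groups the cohort exists to capture under 5.1, and 5.1 asks for the same data on them as on RCT patients. The loss would therefore be selective: the cohort would lose its non-closeable wounds and keep mainly late presenters with closeable ones. The record of who was excluded, and why, would be wrong in the same way.

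**Working it through.** The protocol states no figure on this point, so the check is a comparison of texts.

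**Step 1: same patient, same moment.** In each row the wound has been judged not primarily closeable after debridement.

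| Patient | Under 6.2 | Under the other sections |
|---|---|---|
| Presented within 24 hours, entered as RCT | Excluded from the study, form closed | Cohort (5.4 and 5.7 directly; 5.1 and 6.1 by general rule) |
| Presented after 24 hours, entered as cohort | Excluded; a box ends cohort eligibility | Cohort (5.7 table; 5.1 and 6.1 cover late and non-closeable together) |
| Entered the cohort because the wound was already judged non-closeable | Excluded once closeability is answered No | Cohort (5.1, 5.4, 5.7, 6.1) |

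The outcomes differ in every row. Two places contradict 6.2 directly at the post-debridement check: 5.4 and the 5.7 table. Sections 5.1 and 6.1 support them but are written for screening.

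**Step 2: can 6.2 mean exclusion from the RCT only?** No. The form is declared to cover both groups, item 2b treats closeability as a condition for both, item 2c speaks of the study as a whole, and the second box names the cohort. No step moves the patient across.

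**Step 3: is this only the change log against current text?** No. Sections 6.2, 5.4 and 5.7 are all current. The entry of 3 February 2016 in the Summary of Changes, which widened the cohort to non-closeable wounds, may explain 6.2 as leftover wording, but it is not one side of the conflict.

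**Step 4: can staff carry out 5.4 with the forms as described?** Not cleanly. A patient screened as closeable and presenting within 24 hours is RCT-eligible on the enrollment form. Moving that patient to the cohort while the screening answers stand meets the wrong-study warnings described in 6.1 and 6.2, which tell staff not to proceed until the mismatch is resolved. The 6.2 boxes forbid changing what was already collected. Closing the form at this point also cuts off its later items: damage control, added antibiotics, wound length and OTA wound classification.

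**Step 5: size.** Under 5.6 the patient is randomized only after the wound is judged closeable, so under either rule this patient is never randomized. Randomized patients affected: 0. The requirement in 4.2 (2 × 88 = 176 with completed follow-up) and the expected enrolment of about 240 do not change. The protocol gives no expected number of cohort patients or of closure failures after debridement, so no cohort count is estimated.

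**The case against.** The strongest reply is that little hangs on this. The aims, the null hypothesis, the primary outcome and the sample size do not mention the cohort, which 5.1 calls separate, and the randomized comparison is the same under either rule. The intended rule is also clear: 5.1, 5.4, 5.7 and 6.1 all send these patients to the cohort, and 6.2 looks like a form description that was not updated. The two boxes may be alternatives shown by enrolment type. In that case an RCT patient sees only the loss of RCT eligibility, and that line by itself is compatible with 5.4. Section 6.1 already has staff confirm the assigned study against the calculated one. Nothing in the protocol shows that any record was misclassified.

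Most of this stands as a limit on importance, and none of it removes the contradiction. Item 2c is prose and conflicts with 5.4 without the boxes. Even if the boxes are alternatives, the first still labels the RCT patient an exclusion and closes the form, and the second contradicts 5.1 for the cohort patient. The confirmation step in 6.1 does not provide a route after debridement, because the 6.2 boxes say to leave the collected data as they are.

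**Conclusion.** The concern holds. Section 6.2 gives a rule that 5.4 and the 5.7 table reverse at the same decision point, and 6.2 is out of line with the rest of the protocol. The text should be corrected, but the matter does not threaten the trial's main result: 0 randomized patients are affected, and power and the stated aims are untouched. The harm is confined to who is in the non-randomized cohort, their follow-up data and the recorded exclusions, and its extent cannot be sized from the protocol. The conclusion concerns the written text. The live REDCap logic is not shown, so which records trigger which box, and whether any patient was in fact lost this way, is unknown.

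**What to change.** Reconcile 6.2 with 5.1, 5.4 and 5.7:

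1. Rewrite items 2b and 2c and both warning boxes so that a non-closeable wound means not eligible for randomization, enter or remain in the cohort, and complete the remaining forms and follow-up.
2. Add a sentence on how the assignment changes from RCT to cohort after debridement, including which screening answer is updated so that the wrong-study warnings clear. Section 6.1 keeps both groups in one REDCap project and arm, so this changes an assignment and does not move a record.
3. Check that the live form logic agrees with the corrected text.
4. Review any records already closed as intra-operative exclusions for cohort inclusion where consent allows. Section 5.1 uses one consent form but has the cohort explained in place of the RCT, so a patient consented for the RCT may not have had that explanation. Separate records from before 3 February 2016, since they predate the widening of the cohort and the change log already plans contact with those patients.

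The first two steps remove the contradiction; the last two are checks on its consequences. The cost is two form items, two message boxes, one sentence, one logic check and a limited record review. No data collection is added beyond what 5.1 already plans, and no clinical rule changes.

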5.5 Damage Control

After assessing the wound, the primary surgeon will need to determine if “damage control” using a temporary external fixator is necessary. This may be utilized in situations where the patient is hemodynamically unstable and needs quick stabilization of the tibia or requires another surgery that is more important. This option is available to the surgeon for both RCT and cohort patients. Furthermore, this option is available for RCT patients who are randomized to either a nail or an exfix.

If the surgeon decides to perform damage control, a temporary external fixator will be placed, and the patient will be allowed to recover in the ward with the definitive operation performed at a later date. The date of both the temporary exfix placement and the definitive operation will be recorded onto REDCAP. There is no set time limit or criteria for how long the temporary external fixator should remain on before the definitive treatment is to be conducted. The only standardized policy is that the definitive operation should take place in a timely manner after the clinical issue that warranted the temporary external fixator in the first place has been resolved.

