The patient **IS** eligible for the RCT but has been enrolled in the COHORT study. Because of this, the randomization window module will not appear.

Please double check the inclusion/exclusion criteria. Do not proceed until this error has been resolved.

- b. For RCT patients, this is what the randomization module appears like. Click on randomize, confirm the warning message, and randomize the patient. The randomization module results are final. Once randomization has been performed, the patient must remain in the study and must receive that operation

THIS IS THE RANDOMIZATION MODULE. ONCE YOU RANDOMIZE, THE RESULTS ARE FINAL

This patient has been randomized to receive:

* must provide value

Date and Time of Randomization

* must provide value

Insert date and time by clicking on the calendar image above

4. Damage Control

- a. If the patient believes that damage control using a temporary external fixator should be performed before the definitive operation that the patient has been randomized to (in the case of RCT patients) or that the surgeon has decided (in the case of cohort patients), then record "Yes". Damage control is usually done in situations where the patient is not hemodynamically stable enough for a full surgery, but it is still better to temporarily fixate the fracture using an exfix.

Variable: random [Branching logic exists]

THIS IS THE RANDOMIZATION MODULE. ONCE YOU RANDOMIZE, THE RESULTS ARE FINAL

This patient has been randomized to receive:

* must provide value

Date and Time of Randomization

* must provide value

Will the surgeon perform "damage control" using an external fixator because the patient is currently too unstable?

* must provide value

The patient will now receive a temporary external fixator and receive the definitive operation at a later date. This is allowed under our study protocol.

Please remember to record the dates of both operations in the post-op/discharge form.

reset

5. At this time, additional antibiotics can be added or removed depending on how much contamination the surgeon believes there to be inside the wound

Does the surgeon believe additional antibiotics are required?

+ Gentamycin
 + Gentamycin + Metronidazole
 Other
 No

If "Other", please describe the following:

- Type of antibiotic
- Dosage
- Timing

Expand

6. Wound Characteristics

- Record the wound measurement details here in centimeters
- OTA wound classification performed by surgeon

Wound Measurement	

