By placing a tick in one box in each group below, please indicate which statements best describe your own health state today.

Mobility

I have no problems in walking about

I have some problems in walking about

I am confined to bed

Self-Care

I have no problems with self-care

I have some problems washing or dressing myself

I am unable to wash or dress myself

Usual Activities (e.g. work, study, housework, family or leisure activities)

I have no problems with performing my usual activities

I have some problems with performing my usual activities

I am unable to perform my usual activities

Pain / Discomfort

I have no pain or discomfort

I have moderate pain or discomfort

I have extreme pain or discomfort

Anxiety / Depression

I am not anxious or depressed

I am moderately anxious or depressed

[figure not shown]
I am extremely anxious or depressed

To help people say how good or bad a health state is, we have drawn a scale (rather like a thermometer) on which the best state you can imagine is marked 100 and the worst state you can imagine is marked 0.

We would like you to indicate on this scale how good or bad your own health is today, in your opinion. Please do this by drawing a line from the box below to whichever point on the scale indicates how good or bad your health state is today.

Your own health state today

Best imaginable health state

Worst imaginable health state

UCSF-MOI Open Tibia Fracture Study – OTA Wound Classification

As part of the study, we are collecting data on the types of wounds that our study participants have. Please fill out this handout after the operation. Leave it in the patient's file after you have filled it out. If you have any questions, please contact the study phone at [name].

Patient Name: _____ MRN: _____

Wound measurement (take the maximum length): _____ cm

Skin	 Laceration with edges that approximate  Laceration with edges that DO NOT approximate  Laceration associated with extensive degloving
Muscle	 No muscle necrosis OR some injury with function intact  Loss of muscle but remains functional OR localized necrosis in injured area that requires excision  Dead muscle, loss of function, partial or complete compartment excision, complete disruption disruption of muscle-tendon unit, muscle injury not approximatable

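### Form 6.2 and the wound handout let the OTA wound grade and the post-debridement antibiotic choice be made or recorded after the allocated implant is known

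*Protocol*

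**What the plan says.** The protocol describes the same theatre sequence in three places.

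- **Section 5 (procedures).** Section 5.4 says: "Wound classification is to be done after surgical debridement which allows the surgeon to fully assess the wound". Section 5.1, under antibiotics administration, lets the surgeon add antibiotics after evaluating the wound at debridement. Section 5.6 then randomizes once the wound is judged closeable, and names no other precondition.
- **Section 6.2 (intra-operative form).** After debridement and the closeability judgment, item 2 says: "If it is an RCT patient, proceed to the randomization module". Item 3 says: "Click on randomize, confirm the warning message, and randomize the patient", and the result is final. Only then come damage control (item 4), antibiotics (item 5: "At this time, additional antibiotics can be added or removed depending on how much contamination the surgeon believes there to be inside the wound") and the OTA wound classification by the surgeon (item 6).
- **Appendix (OTA wound classification handout).** The surgeon is told: "Please fill out this handout after the operation".

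No section requires the grade or the antibiotic judgment to be saved before the allocation is shown.

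**The concern.** The surgeon cannot be blinded to the implant. Concealment up to the randomize button is therefore the only protection for judgments that are meant to describe the wound as it was before treatment. Two such judgments sit on the wrong side of that button on the form.

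The first is the OTA grade of skin, muscle, arterial injury, contamination and bone loss. Aim 3 (section 3) looks for injury-related predictors of reoperation, return to work and quality of life, and this grade is a natural candidate. Section 2.2 reports that earlier literature favoured external fixation as severity rose. A grade given with the implant known is exposed to that association. If grades shift by arm, the baseline comparison and any prognostic model that uses them are distorted, and this cannot be repaired afterwards.

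The second is the intra-operative antibiotic choice. Repeat debridement for infection is a primary event and deep infection is a secondary outcome (section 4.1). If antibiotics were intensified more often in one arm because the implant was known, part of the difference between arms would belong to the antibiotics.

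**Working it through.** **1. The three descriptions side by side**

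| Step | Section 5 | Form 6.2 | Handout |
|---|---|---|---|
| Wound length | 5.4: measured ahead of debridement | measured at item 1, entered at item 6 | has a line for it |
| Closeability | 5.4 and 5.6: after debridement, triggers randomization | item 2 | none |
| Allocation revealed | 5.6 | item 3 | none |
| Damage control | 5.5: after wound assessment | item 4 | none |
| Added antibiotics | 5.1: on evaluation at debridement | item 5 | none |
| OTA wound grade | 5.4: after debridement | item 6 | after the operation |

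For the grade and the added antibiotics, section 5 sets an earliest time (debridement) but no latest time. The permitted window therefore runs across the moment of allocation. The form and the handout both point to the later part of it.

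**2. One judgment, two uses.** Section 5.1 sets the antibiotic regimens by contamination level, at the surgeon's discretion. Contamination is also one of the five OTA items. A single unblinded view of the wound can thus drive both a treatment and a baseline variable. As the form is reproduced in the protocol, wound length and damage control carry a must-answer mark. The antibiotic question and the OTA items do not, so they could be left and completed later.

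**3. What stays clean.** Wound length is measured with a ruler before debridement (5.4). Fracture classification is read from pre-operative films (5.2). The first antibiotic regimen is chosen at admission (5.1). None of these depends on the form order.

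**4. The plan's own figure.** Inputs from section 4.2: 5% against 20%, power 80%, alpha 0.05 (taken as two-sided), 88 per group.

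- Uncorrected: [1.96·√(2·0.125·0.875) + 0.842·√(0.05·0.95 + 0.20·0.80)]² / 0.15² = 75.1, so 76.
- With continuity correction: (75.1/4)·[1 + √(1 + 4/(75.1·0.15))]² = 87.9, so 88.

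The stated 88 reproduces, and nothing here changes it.

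**5. Size of the antibiotic route, with assumed inputs.** The documents give no figure, so this only shows a scale.

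- Infection risk: about 10%, the middle of the pilot's 7.7% (nail) and 12.5% (external fixation) in section 2.3.
- Excess use of added antibiotics in one arm: 10 to 30 percentage points (assumed).
- Relative reduction in infection from the added antibiotics: 20% to 50% (assumed).

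Spurious difference = risk × excess use × relative reduction.

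- Low: 0.10 × 0.10 × 0.20 = 0.002, or 0.2 points.
- High: 0.10 × 0.30 × 0.50 = 0.015, or 1.5 points.

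Against the planned 15 points this is 0.2/15 = 1.3% to 1.5/15 = 10%. Against the pilot difference in deep infection (12.5 − 7.7 = 4.8 points) it is 4% to 31%.

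**6. Effect on the primary test.** Assume no implant effect, 12.5% reoperation in each arm (the mean of the planning rates), 88 per arm, and a shift d in one arm. The rejection rate is Φ[(d − 1.96·SE₀)/SE₁] + Φ[(−d − 1.96·SE₀)/SE₁], with pooled SE₀ and unpooled SE₁. At d = 0.01 both are about 0.049, which gives 5.5%. At d = 0.02 it is 7.0%, against 5.0% with no shift. This treats every shifted infection as a reoperation, so it overstates the effect of the range in step 5.

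**7. Size of the grading route.** It cannot be put in risk points. The documents say nothing about how far grades might move.

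**The case against.** **Form order is not decision order.** Wound length shows this: it is measured before debridement yet entered at item 6. Form 6.2 is also not fully aligned with section 5, since it excludes wounds that cannot be closed while 5.4 sends them to the cohort study. This stands. A reader might infer that surgeons do decide and grade after seeing the allocation, and the documents do not show that. They show that nothing prevents it, and that the handout asks for a late grade.

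**Damage control can properly depend on the allocation.** A reader might add it as a third compromised decision. Item 4 asks whether "damage control using a temporary external fixator should be performed before the definitive operation that the patient has been randomized to", and section 5.5 adds: "Furthermore, this option is available for RCT patients who are randomized to either a nail or an exfix". Section 2.2 describes nailing as the longer operation and external fixation as quick to apply. Whether a patient is stable enough for the allocated operation can depend on which one it is, so staging that differs by arm may belong to the strategies being compared. This stands, and damage control is not part of the finding.

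**The randomized comparison does not use the grade.** Section 5.6 describes blocks with no stratification by wound grade, and no section makes the grade a covariate for the primary outcome. This also stands. The exposure is in the baseline description and Aim 3. Bone loss, moreover, has a separate radiographic field on the baseline image form (6.3).

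**The antibiotic route is narrow and would not be fully closed.** The first regimen precedes allocation. Ward staff may add antibiotics later and the surgeon may stop a course (5.1). Both named intra-operative additions on the form contain gentamicin, and the appendix on supply reports that little of it was used. A 30-point difference between arms therefore looks unlikely, although patients could buy later doses themselves. This limits the size but does not remove the inconsistency.

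**Conclusion.** The point holds in a limited form. Sections 5.1 and 5.4, form 6.2 and the handout do not agree on when the OTA grade and the post-debridement antibiotic judgment are made. The form and the handout allow both to follow the allocation in an open-label trial. The main exposure is a baseline severity measure relevant to Aim 3. The lesser one is an unequal co-intervention.

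Neither is a demonstrated effect. The figures of 0.2 to 1.5 points, and of 5.5% to 7.0% rejection for a shift of 1 to 2 points, rest on assumed inputs and have no established direction. A reader might infer that baseline severity as a whole is compromised, or that the primary comparison is biased. The documents support neither. This is a cheap improvement, worth making because late grades cannot be recovered.

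**What to change.** Reconcile section 5.1 (antibiotics), section 5.4, form 6.2 and the handout on timing:

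- Make the OTA wound classification and the post-debridement antibiotic judgment mandatory, time-stamped fields, saved after debridement and before the REDCap randomize button appears.
- Change the handout instruction to completion after debridement and before randomization.
- Leave later antibiotic changes allowed, and log each with its reason and time.
- State in sections 5.5 and 6.2 when damage control is recorded. It need not be fixed before allocation.
- For patients enrolled before the change, report the wound grade as one that may have been recorded after allocation.

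This concerns when judgments are recorded. No regimen or clinical rule changes. The cost is a change to the form's field order and branching, one line on the handout, and a short delay in theatre before randomization. It needs no new data items or staff, since the coordinator already attends in theatre to randomize.
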